7.5 Informed Consent

The Investigator must obtain documented consent from each potential subject prior to participating in a clinical trial.

Consent must be documented by the subject's dated signature on a consent form along with the dated signature of the person conducting the consent discussion.

A copy of the signed and dated consent form should be given to the subject before participation in the trial.

The initial informed consent form, any subsequent revised written informed consent form and any written information provided to the subject must receive the IRB/ERC's approval/favorable opinion in advance of use. The subject should be informed in a timely manner if new information becomes available that may be relevant to the subject's willingness to continue participation in the trial. The communication of this information will be provided and documented via a revised consent form or addendum to the original consent form that captures the subject's dated signature.

Specifics about a trial and the trial population will be added to the consent form template at the protocol level.

The informed consent will adhere to IRB/ERC requirements, applicable laws and regulations and Sponsor requirements.

7.6 Trial Procedures

See the Schedule of Events for when tests should be completed.

Clinical procedures:

- Demographics
- Medical history
- Prior medication review
 - The investigator or qualified designee will review prior medication and herbal and dietary supplement use, including any protocol-specified washout requirement, and record prior medication taken by the subject within 28 days before starting the trial. Treatment for the disease for which the subject has enrolled in this study will be recorded separately and not listed as a prior medication.
 - The investigator or qualified designee will record medication, if any, taken by the subject during the trial. All medications related to reportable SAEs and ECIs should be recorded.
 - Subjects will be asked to stop all nonprescription herbal supplements and over the counter medication.
- Full physical examination
- Vital signs
 - temperature, pulse, respiratory rate, height, weight and blood pressure. Height will be measured at screening only.
- ECOG performance status (Appendix)
- Archival tissue collection:
 - If available, any tumor biopsy tissue (lung, mediastinal, or brain) that was obtained prior to screening for the study will be requested and sent to the Merck-designated Contract Research Organization (CRO) QualTek Molecular Laboratories for PD-L1 biomarker assay.
- Biopsy or resection of metastatic brain lesion
 - When clinically indicated, a biopsy or resection will be done of the brain lesion(s) 1) prior to enrollment and SRS, and 2) at the time of persistent radiographic progression. Any tumor biopsy tissue will be sent to the Merck-

designated Contract Research Organization (CRO) QualTek Molecular Laboratories for PD-L1 biomarker assay.

- At persistent radiographic progression, a repeat biopsy or resection is considered standard of care to distinguish true vs pseudoprogression.
- Standard of care therapy:
 - Arm 1: All patients will receive standard of care stereotactic radiosurgery in 1-5 fractions, at the discretion of the treating radiation oncologist. If all lesions cannot be treated on the same day, all lesions MUST be treated ≤ 14 days of treatment of the first lesion. Gamma knife or X-rays with nominal energy of 4 megavoltage (MV) or greater for accelerator-based treatments, including isocentric conical collimators, mini-multi-leaf (5mm or less) technology or linear accelerators mounted on robotic arms will be used to deliver the target dose .
 - Target Volume: The volumes shall be defined by a planning MRI brain scan, with the patient in the treatment position. The target volume should include the enhancement seen on planning MRI with 0-1 mm margin. The maximal cross-sectional diameter must be < 3.0 cm for a lesion treated with a single fraction.
 - Target Dose: The dose should be prescribed to the highest isodose line encompassing the 90-95% target volume. General dose guidelines are as follows
 - Lesion diameter < 1 cm – 20-22 Gy in 1 fraction
 - Lesion diameter 1-2 cm – 18-20 Gy in 1 fraction
 - Lesion diameter 2-3 cm – 18 Gy in 1 fraction, or 27 Gy in 3 fraction or 30-35 Gy in 5 fractions
 - Lesion diameter 3-5cm – 30 – 35 Gy in 5 fractions
 - Up to 8 of dexamethasone can be administered on the day of single fraction SRS, at the discretion of the treating physician.
 - Arm 2:
 - All patients in this arm will be treated with standard of care radiotherapy consisting of fractionated focal irradiation to gross tumor volume (GTV) plus a up to 3-cm margin at a dose of up to 2-Gy per fraction given once daily five days per week (Monday through Friday) over a period of six weeks, for a total dose of up to 60 Gy.
 - Additionally, standard of care temozolamide 75 mg/m² once daily (Monday through Sunday) over the 6 weeks duration of radiation. After a 4-week break, subjects will then receive up to six cycles of adjuvant temozolomide according to the standard 5-day schedule every 28 days (150 mg/m² for the first cycle and then increased to 200 mg/m² beginning with the second cycle, as long as there were no hematologic toxic effects as per Stupp et al 2005 [80]. Dose modifications for temozolomide are described in section 7.13.
 - Radiation therapy to an additional symptomatic solitary lesion or to the brain may be allowed at the investigator's discretion at any time during the study if :
 - they fulfill other criteria to remain in the study and

- this lesion has remained stable or shows radiographic response compared to baseline.
- this additional lesion was not in the initial radiation field.

Subjects may continue with pembrolizumab even if radiation or chemotherapy is discontinued, at the discretion of the PI.

Additionally, subjects may receive prophylaxis against *Pneumocystis carinii* pneumonia, consisting of either inhaled pentamidine or oral trimethoprim–sulfamethoxazole, at the physician’s discretion [89].

Subject may also provide consent/assent for future correlative research (optional). Subjects may participate in the main trial without participating in future correlative research.

Lab tests (see Table 5):

- CBC with differential
- Comprehensive serum chemistry panel
- Urinalysis
- FT4, TSH
- PT/INR
- aPTT
- Pregnancy test (urine or serum) (women). If the urine test is positive, cannot be performed or cannot be confirmed as negative, a serum pregnancy test will be required.
- Serum biomarker assay (see Section 8.3.1)

Table 5 Laboratory Tests

Hematology	Chemistry	Urinalysis	Other
Hematocrit	Albumin	Blood	Serum β -human chorionic gonadotropin [†]
Hemoglobin	Alkaline phosphatase	Glucose	(β -hCG) [†]
Platelet count	Alanine aminotransferase (ALT)	Protein	PT (INR)
WBC (total and differential)	Aspartate aminotransferase (AST)	Specific gravity	aPTT
Red Blood Cell Count	Lactate dehydrogenase (LDH)	Microscopic exam (If abnormal)	Free thyroxine (T4)
Absolute Neutrophil Count	Carbon Dioxide \ddagger	results are noted	Thyroid stimulating hormone (TSH)
Absolute Lymphocyte Count	(CO_2 or biocarbonate)	Urine pregnancy test [†]	
	Calcium		Blood for correlative studies
	Chloride		
	Glucose		
	Potassium		
	Sodium		
	Total Bilirubin		
	Direct Bilirubin (If total bilirubin is elevated above the upper limit of normal)Total Bilirubin		
	Total protein		

Laboratory tests for screening or entry into the Second Course Phase should be performed within 10 days prior to the first dose of treatment. After Cycle 1, pre-dose laboratory procedures can be conducted up to 72 hours prior to dosing. Results must be reviewed by the investigator or qualified designee and found to be acceptable prior to each dose of trial treatment.

Imaging (all timepoints +15 days)

Standard of care clinical brain MRI: Clinical MRIs are done at baseline, 4 weeks after the last day of radiation and then every 9 weeks (see special instructions below for evaluating persistent radiographic progression). Gadolinium is the preferred contrast agent, when subject qualifies (per institutional policy, see section 8.2.2) for gadolinium infusion, but is not required.

Ferumoxytol MR (FeMRI): ferumoxytol steady state MRIs of the brain are done baseline, 4 weeks after the last day of radiation, anytime there is suspected radiographic progression and 4 weeks after suspected radiographic progression. Additional optional MR imaging of systemic lesions for subjects in Arm 1 may be performed in the same setting and time points as the brain imaging. Details are explained in section 8.2.3.

Evaluation of systemic disease burden (only for Arm 1): A standard of care PET/CT or CT abdomen, chest and pelvis with contrast will be obtained within 3 months of enrollment and at least every 6 months thereafter. This is considered standard of care for patients with systemic cancer. Stable systemic disease burden should be demonstrated at enrollment and for continuation of study drug.

Imaging Schedule (all timepoints +15 days)

Arm 1: All patients will be scanned with clinical MRI at baseline prior to radiation, 4 weeks after the last day of radiation and there after every 9 weeks. Ferumoxytol steady state MRI (FeMRI) will be performed in the same sitting at baseline and 4 weeks after the last day of radiation. Thereafter, FeMRI may be performed independent of the clinical MRI if there is suspected radiographic progression or to confirm radiographic progression. Patients enrolled in ARM 1 may be concomitantly enrolled into additional brain tumor imaging studies conducted at OHSU.

Arm 2: All patients will be scanned with clinical MRI at baseline prior to radiation, 4 weeks after the last day of radiation and there after every 9 weeks. FeMRI will be performed in the same sitting at baseline and 4 weeks after the last day of radiation. Thereafter, FeMRI may be performed independent of the clinical MRI if there is suspected radiographic progression or to confirm radiographic progression. If there is suspected progression, subjects undergo a ferumoxytol steady state MRI and continue on pembrolizumab for one more cycle (total of 4 weeks). At the 4 week point, clinical standard of care and ferumoxytol MRIs will be repeated to confirm persistent radiographic progression. If the 4 week scan confirms progression, then pembrolizumab is discontinued and subject is evaluated for surgery. If histopathology confirms pseudoprogression or is inconclusive, the subject will continue on pembrolizumab every 3 weeks until further radiographic progression is suspected. If histopathology confirms progression, the subject will be removed from the study.

Contrast agents dosing and administration

Clinical Standard of Care MRI: Gadoteridol enhanced MRI will be used per institutional guidelines (see section 8.2.2). In subjects that are already enrolled and have underwent at least one gadolinium enhanced MRI, but do not qualify to get Gadolinium at subsequent imaging time points, non-contrast enhanced MRI can be used as clinical MRI.

Dosing of Gadoteridol: After acquiring precontrast images, gadoteridol (Prohance®, Bracco Pharm) will be injected using a power injector. An IV bolus of 0.1 mmol/kg at a flow rate of up to 3 mL/s will be administered, followed by a saline flush during the first DSC sequence. The appropriate volume of gadoteridol is based on the subject's weight (0.2 ml/kg gadoteridol = 0.1 mmol/Kg) followed by a 20ml saline flush.

Ferumoxytol Imaging

Ferumoxytol imaging consists of two consecutive days of imaging (early and delayed) and will be performed only at time points described in the study schema.

Early intravascular phase scan ferumoxytol imaging

Dosing of ferumoxytol: The total dose of ferumoxytol (AMAG Pharmaceuticals, Inc., Cambridge MA) will be 7mg/kg (not exceeding 510mg total). The ferumoxytol will be mixed with normal saline 1:1 solution to dilute to 15mg/ml. 1 mg/Kg IV will be injected at the start of the 7th dynamic cycle during the DSC acquisition at a flow rate of 3ml/s followed by 20ml saline flush. The rest of the ferumoxytol will be given as IV injections at a low flow rate (1ml/s) followed by 20mg saline flush. The flow rates may be adjusted at the physician's discretion.

Delayed (18-72h) parenchymal phase ferumoxytol scan - Optional

No contrast agent will be given during this MRI. This scan is optional. Every effort will be made to schedule the scan as close to 24 hours after ferumoxytol as possible.

Image processing

Image processing will be done at OHSU. SS-CBV maps will be created using the high resolution T2*w scans before and after contrast agent and $\Delta R2^*$ maps will be created using the formula $\Delta R2^* = \ln(SI_{pre}/SI_{post})/TE$, in which SI_{pre} and SI_{post} indicate the signal intensities pre- and post ferumoxytol, and TE is the echo time. When gadolinium is given, DSC-CBV maps from gadoteridol DSC will be created using a mathematical leakage correction method in NordicICE (Nordic Neurolab, Bergen, Norway) an FDA approved perfusion MRI software. The coregistration and overlay of CBV maps on T1-w MPRAGE will be done using NordicICE as well [90, 91]. The clinical MR sequences, such as T1 weighted scans with and without gadoteridol, and T2 weighted pre contrast scans will also be read. Images will be read by 2 radiologists. The radiologists will be blinded to the type of CBV maps (SS and DSC) and subject information

Adverse Event Monitoring

The investigator or qualified designee will assess each subject to evaluate for potential new or worsening AEs as specified in the Schedule of Events and more frequently if clinically indicated. Adverse experiences will be graded and recorded throughout the study and during

the follow-up period according to NCI CTCAE Version 4.0. Toxicities will be characterized in terms regarding seriousness, causality, toxicity grading, and action taken with regard to trial treatment. All AEs will be attributed to pembrolizumab or ferumoxytol separately.

For subjects receiving treatment with pembrolizumab all AEs of unknown etiology associated with pembrolizumab exposure should be evaluated to determine if it is possibly an event of clinical interest (ECI) of a potentially immunologic etiology (termed immune-related adverse events, or irAEs); see the separate ECI guidance document regarding the identification, evaluation and management of potential irAEs.

Please refer to Section 9 for detailed information regarding the assessment and recording of AEs.

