5.2 Subject Inclusion Criteria

In order to be eligible for participation in this trial, the subject must:

1. Be willing and able to provide written informed consent/assent for the trial.
2. Be ≥ 18 years of age on day of signing informed consent.
3. Have a life expectancy of at least 6 months.
4. Have a histologically confirmed diagnosis of: newly diagnosed glioblastoma (WHO Grade IV)
5. Have ECOG performance status of 0 or 1 on stable or reducing dose of steroids for symptom management (not more than 8 mg of dexamethasone or equivalent per day) for 5 days prior to enrollment. Change in glucocorticoid dose for any purpose other than to modulate symptoms from an adverse event. *Note: The use of physiologic doses (e.g., prednisone 10 mg) of corticosteroids may be approved after consultation with Merck & Co. Use of prophylactic corticosteroids to avoid allergic reactions (e.g. IV contrast dye) is permitted.*
6. At least 14 days from any major surgeries including brain biopsy before the start of study drug pembrolizumab.
7. Demonstrate adequate organ function as defined in Table 3.
8. Female subject of childbearing potential should have a negative urine or serum pregnancy within 72 hours prior to receiving the first dose of study medication. If the urine test is positive or cannot be performed or confirmed as negative, a serum pregnancy test will be required.
9. Female subjects of childbearing potential should be willing to use 2 methods of birth control or be surgically sterile, or abstain from heterosexual activity for the course of the study through 120 days after the last dose of study medication. Subjects of childbearing potential are those who have not been surgically sterilized or have not been free from menses for > 1 year. Male subjects should agree to use an adequate method of contraception, including but not limited to, abstinence from heterosexual activity starting with the first dose of study therapy through 120 days after the last dose of study therapy.
10. Subject is eligible for and agrees to receive standard of care radiation and temozolamide after biopsy or maximum safe surgical resection.

Table 3 Adequate Organ Function Laboratory Values

System	Laboratory Value
--------	------------------

Hematological	
Absolute neutrophil count (ANC)	≥1,500 /mcL
Platelets	≥100,000 / mcL
Hemoglobin	≥9 g/dL or ≥5.6 mmol/L without transfusion or EPO dependency (within 7 days of assessment)
Renal	

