5.3 Subject Exclusion Criteria

The subject must be excluded from participating in the trial if the subject:

1. Has a diagnosis of immunodeficiency including Human Immunodeficiency Virus (HIV) (HIV 1/2 antibodies) and is not on continuous daily immunosuppressive therapy within 7 days prior to the first dose of trial treatment. (An exception to this is the use of steroids for brain edema and resulting symptoms. Subjects may receive a stable or reducing dose of steroids (up to 8 mg dexamethasone or equivalent for at least 5 days prior to signing consent) to prevent or manage cerebral edema. Subjects requiring over 8mg of dexamethasone per day on or five days prior to signing consent are excluded).
2. Has a known history of active TB (Bacillus Tuberculosis)
3. Hypersensitivity to pembrolizumab or ferumoxytol or any of their excipients.
4. Has had a prior anti-cancer monoclonal antibody (mAb) within 4 weeks prior to study Day 1 or who has not recovered (i.e., ≤ Grade 1 or at baseline) from adverse events due to agents administered more than 4 weeks earlier.
5. Has a known additional malignancy that is progressing or requires active treatment. Exceptions include basal cell carcinoma of the skin or squamous cell carcinoma of the skin that has undergone potentially curative therapy or in situ cervical cancer.
6. Has active autoimmune disease that has required systemic treatment in the past 2 years (i.e. with use of disease modifying agents, corticosteroids or immunosuppressive drugs). Replacement therapy (eg thyroxine, insulin, or physiologic corticosteroid replacement therapy for adrenal or pituitary insufficiency, etc.) is not considered a form of systemic treatment.
7. Has known history of, or any evidence of active, non-infectious pneumonitis.
8. Has an active infection requiring systemic therapy.

9. Has a history or current evidence of any condition, therapy, or laboratory abnormality that might confound the results of the trial, interfere with the subject's participation for the full duration of the trial, or is not in the best interest of the subject to participate, in the opinion of the treating investigator.
10. Has known psychiatric or substance abuse disorders that would interfere with cooperation with the requirements of the trial.

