6.0 SCHEDULE OF EVENTS

	Screening visit: within 28 days of first treatment	Pembro infusion every 3 weeks +15 days	At suspected radiographic progression (+15 days)	At persistent radiographic progression (+15 days)	Safety follow-up: 30 days (+15 days) post discontinuation of pembro	Follow-up: those who complete 2 years of treatment or 35 cycles	Survival: follow-up once off study ⁸
Informed Consent	X						
Inclusion/Exclusion Criteria	X						
Archival Tissue Collection (if available)	X						
Standard of Care Biopsy or Resection of Brain Lesion ¹				X			
Demographics and Medical History	X						
Medication, herbal or dietary supplement review	X		X	X	X	X	
Review Adverse Events, include Events of Clinical Interest ¹⁰			X	X	X	X	
Physical Examination ²	X			X	X	X	
Vital Signs and Weight	X			X	X	X	
ECOG Performance Status	X			X	X	X	
CBC with Differential ³	X	X			X		
Comprehensive Serum Chemistry Panel (with LDH) ³	X	X			X		
Urinalysis	X						
FT4 and TSH ⁴	X	X			X		
PT/INR, aPTT	X				X		
Pregnancy Test (urine or serum/males only – see section 7.6)	X						
Clinical Tumor Imaging	X ⁵					X ⁷	
Ferumoxytol imaging	X ⁶						
24 hr post study drug MRI - Optional	X ⁶						
Biomarker Collection (serum) Optional	X ⁶						
Post-study anticancer therapy status						X	
Survival Status						X	X
Telephone contact							X ⁸

¹Subjects must undergo standard of care biopsy or maximal safe resection as clinically indicated prior to enrollment.

²Physical exam required with every pembrolizumab infusion.

³CBC and CMP (with LDH) to be done every 3 weeks while on pembrolizumab - labs must be done within 28 days before first pembrolizumab infusion, and within 72 hours of subsequent pembrolizumab infusions. Additional labs may be drawn at treating physician's discretion.

⁴FT4 and TSH with every cycle while on pembrolizumab.

⁵Clinical standard of care MRIs are done at baseline, 4 weeks after the last day of radiation and then every 9 weeks (see special instructions below for evaluating persistent radiographic progression). Clinical MRIs may be done more often at physician's discretion.

⁶Ferumoxytol steady state MRIs (within 7 days of clinical standard of care MRIs) are done baseline, 4 weeks after the last day of radiation, anytime there is suspected radiographic progression and 4 weeks after suspected radiographic progression (all timepoints ± 15 days). Serum biomarkers will be obtained ± 15 days of ferumoxytol MRI scan.

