7.0 TREATMENT PLAN AND PROCEDURES

7.1 Participant Screening and Enrollment

In order to participate in this study, signed informed consent must be obtained from the participant. The current Institutional Review Board (IRB) approved informed consent must be signed and dated by each participant prior to undergoing any study procedures or before any prohibited medications are withheld from the participant in order to participate in this study.

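### Two entry rules fail as written: the permitted age of screening labs is 28 days in one section and 10 in another, and the albumin limit of 2.5 mg/dL can exclude nobody

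*Combined protocol and SAP*

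**What the plan says.** **Age of screening labs.** In the Schedule of Events (section 6.0) the screening column is headed "Screening visit: within 28 days of first treatment". Footnote 3, on the blood count and the chemistry panel, says "labs must be done within 28 days before first pembrolizumab infusion, and within 72 hours of subsequent pembrolizumab infusions". Section 7.6, just after Table 5, says "Laboratory tests for screening or entry into the Second Course Phase should be performed within 10 days prior to the first dose of treatment". The pregnancy test has its own window in inclusion criterion 8, "within 72 hours prior to receiving the first dose of study medication", and is not in dispute.

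**Which section governs.** Section 7.6 opens by sending the reader to the Schedule for the timing of tests. Section 7.2 calls the Schedule a summary and says that the individual procedures are set out in detail afterwards. The cross-references point both ways.

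**Albumin.** Table 3 in section 5.2 requires albumin of at least 2.5 mg/dL. The same table gives hemoglobin in g/dL. Section 7.11 applies the section 5.2 organ-function limits again for entry into the Second Course Phase.

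**Dexamethasone (minor).** Inclusion criterion 5 limits the dose to "not more than 8 mg of dexamethasone or equivalent per day) for 5 days prior to enrollment". Exclusion criterion 1 says "Subjects requiring over 8mg of dexamethasone per day on or five days prior to signing consent are excluded".

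**The concern.** Table 3 is where organ function is checked before a subject first receives pembrolizumab with chemoradiation. If two sections disagree on how old the results may be, the person completing the eligibility checklist and the person auditing it can reach opposite answers on the same subject. A draw 20 days before the first dose is valid under one section and a deviation under the other. Section 12.5 provides for an annual audit, so the disagreement would show up as inconsistent deviation counts.

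The albumin line is a different kind of fault. It looks like a criterion, but as printed it does no work: every subject is recorded as meeting it whatever the result.

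What is at stake is consistent eligibility decisions and a clear description of who entered the safety analysis, not the primary estimates of sensitivity and specificity.

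**Working it through.** The plan states no figure on this point to reproduce, so the check compares the passages and adds simple arithmetic.

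1. **Lab window.** Inputs: 28 days (section 6.0, footnote 3) and 10 days (section 7.6), both counted back from the first dose.
   - Width of the disagreement: 28 − 10 = 18 days (ages 11 to 28).
   - Share of the longer window: 18 / 28 = 64%.
   - Labs aged 0 to 10 days satisfy both sections.

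2. **What the oldest permitted labs could predate.**
   - Surgery: inclusion criterion 6 requires at least 14 days between major surgery and pembrolizumab. With surgery at day −14 and labs at day −28, the labs precede surgery by 28 − 14 = 14 days.
   - Temozolomide: section 6.0 lets pembrolizumab start up to 15 days after the first day of radiation, and Table 4 gives temozolomide daily during radiation. Assuming temozolomide starts on radiation day 1, labs 28 days before a first infusion that is 15 days late precede it by 28 − 15 = 13 days.
   - Each result pairs the oldest permitted labs with an extreme permitted date. They are outer bounds, not typical cases.

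3. **Albumin.** Input: 2.5 mg/dL (Table 3).
   - Conversion: 2.5 / 1000 = 0.0025 g/dL.
   - The documents give no range of patient values. Assume 1.0 to 5.0 g/dL, that is 1000 to 5000 mg/dL.
   - Ratio to the printed limit: 1000 / 2.5 = 400 at the bottom of the range and 5000 / 2.5 = 2000 at the top. No value in the range comes near the limit.
   - If 2.5 g/dL was meant, the printed limit is too low by 2500 / 2.5 = 1000. That intention is an assumption.

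4. **Dexamethasone dates.** A subject must meet every inclusion criterion and no exclusion criterion.
   - Above 8 mg at consent, then five days at or below 8 mg by enrollment: meets inclusion 5, barred by exclusion 1. Ineligible.
   - At or below 8 mg at consent and in the five days before, then above 8 mg at enrollment: passes exclusion 1, fails inclusion 5. Ineligible.
   - Both cases have a definite answer, so the two criteria do not contradict each other.

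5. **Effect on section 10.0.** None of these inputs enters the precision calculation. The exact intervals there reproduce: 22/26 gives 65% to 96%, and 15/17 gives 64% to 99%.

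**The case against.** **The Schedule settles the lab window.** Section 7.6 defers to the Schedule for timing, and its 10-day sentence is advisory in form while footnote 3 is mandatory, so 10 days could be a preference inside a 28-day limit. This is a fair reading, but section 7.2 points the other way, and nothing says that the shorter window is optional. Confining the 10 days to the Second Course is strained, because the sentence names screening as well and the next one turns to labs after Cycle 1.

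**The safety consequence is limited.** This largely stands. Section 7.6 also requires the results to be reviewed and accepted before each dose, footnote 3 permits extra labs, and section 7.13 holds concurrent temozolomide on neutrophil and platelet counts, which presupposes that counts are taken. None of these fixes the age of the results used for entry. But a reader might infer that organ function for all 43 glioblastoma subjects rests on pre-operative or pre-chemotherapy values, and the documents do not support that: it takes the stacked extremes shown above.

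**Albumin is only a unit slip.** Probably so. It conflicts with no other albumin limit, and the intended unit is not stated. It is still the operative text of an eligibility criterion.

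**Dexamethasone.** A reader might infer that a subject is admitted or refused according to which criterion is read. As shown, both apply together. Enrollment is also not defined as a date. Section 12.2 assigns a subject code at enrollment and section 12.4 at consent, which hints that the two coincide; section 7.2 makes registration depend on a completed eligibility review, which suggests that they do not. Section 7.1 settles only that "informed consent must be signed and dated by each participant prior to undergoing any study procedures". Nor does the note on physiologic steroid doses in inclusion 5 clearly clash with the 8 mg allowance: the allowance concerns symptoms and edema, and exclusion 6 treats physiologic replacement separately.

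**Conclusion.** Two entry rules are wrong as written. The screening-lab window is stated as 28 days and as 10, leaving 18 days (64% of the longer window) in which one set of results passes one section and fails the other. The printed albumin limit cannot exclude anyone, at entry or at Second Course entry. That conclusion rests on the assumed range of 1.0 to 5.0 g/dL but has a margin of at least 400-fold; the 1000-fold figure further assumes that g/dL was intended.

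The two dexamethasone dates are a minor wording point, not a contradiction. There is no evidence here of bias in the rCBV classification, and no sample-size or precision figure is affected. The faults are worth correcting because they sit in the text used to decide eligibility.

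**What to change.** - State one screening-lab window, counted from the first pembrolizumab dose, in both footnote 3 of section 6.0 and section 7.6. The clinical team chooses it. Until then, labs drawn within 10 days satisfy both sections as they stand.
- Have the sponsor verify the albumin limit and correct its unit in Table 3. Section 7.11 then inherits the correction.
- As a tidying step, use one named date for the dexamethasone condition in inclusion 5 and exclusion 1, or define enrollment.

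The cost is a wording amendment and an updated eligibility checklist. If the shorter lab window is kept, some subjects will need one repeat routine blood draw.
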